13.0 Data and Safety Monitoring Plan

13.2 * DATA AND SAFETY MONITORING PLAN: (REQUIRED)

All greater than minimal risk studies are required to provide a plan. Lack of an adequate plan is one of the most common reasons why IRB approval is delayed.

Instructions:

Describe the plan for monitoring data quality and participant safety. Key areas that should be included in the plan are:

- An explanation of the plan to monitor data collection, study progress, and safety
- A description of who will perform the monitoring and at what frequency (e.g., the PI only, a contract research organization, a Data and Safety Monitoring Board or Data Monitoring Committee, etc.)
- The type of data and events that will be reviewed (e.g., adverse events, breaches of confidentiality, unanticipated problems involving risk to participants or others, unblinded efficacy data, etc.)
- Procedures and timeline for communicating monitoring results to the UCSF IRB, the study sponsor, and other appropriate entities
- Assurance that the research team will adhere to the **UCSF IRB reporting requirements**

As appropriate:

- A plan for conducting and reporting interim analysis
- Clearly defined stopping rules
- Clearly defined rules for withdrawing participants from study interventions

Patients will be monitored as per routine nursing care as well as followed by the acute pain service for the management of the epidural catheter. Any adverse events occurring in a study participant will be managed by the acute pain service and be brought immediately to the principal investigator for review. Given that epidural is routinely performed for the ERAS pathway, we consider this a low-risk study.

Serious or unexpected adverse events will be reported to the CHR within 10 working days in accordance with CHR guidelines.

We are also planning on performing an interim analysis after 44 patients have completed the study to investigate whether there are any differences in outcomes as well as adverse events reported between study groups.

13.3 * DATA AND SAFETY MONITORING BOARD (DSMB): Will a Data and Safety Monitoring Board (DSMB) be established: (REQUIRED)

Yes

No

Guidelines

A Data and Safety Monitoring Board (DSMB) or Data Monitoring Committee (DMC) is a formal, independent committee that is specifically established to conduct interim monitoring, oversight and analysis of study information and data to assure the continuing safety, efficacy, appropriateness, relevance, and integrity of the study.

The UCSF IRB reserves the right to request a DSMB/DMC for any study. However, the following are factors that the IRB will consider when making this determination:

- There is a significant likelihood of a serious adverse event to subjects
- The study is conducted at multiple sites and the level of risk is greater than minimal
- The study generates data that are blinded or randomized
- The study involves a large number of patients randomized to one of two or more interventions

- A study for which the performance of an interim analysis is crucial for the protection of the subjects
- First use in humans
- First use in children
- The study involves gene transfer, stem cell therapy, or other novel interventions for which long-term outcome data are not known or available

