The clinical investigator who enrolled the patient will write the epidural infusion orders. A PACU nurse will be programming the pump following hospital policies. The attending in the acute pain service will be informed about the enrollment of the patient in the study to ensure the pain service has all the information needed to ensure the best pain control to the patient in accordance with the study protocol. The display of the pump will be covered with a removable cover to make sure that the patient will stay blinded about the treatment group. The epidural pumps will subsequently be managed by the acute pain service, not the study investigators. The study protocol allows the reduction of epidural flow rates from 8ml to 6ml/h (from 4ml q30 to 3 ml q30 min in the bolus group) in case of hypotension.

Patients will have the option to administer patient controlled epidural analgesia (PCEA) in addition to the basal rate. For continuous epidural infusion group, they can receive additional 2ml every 15 minutes (lock out period) for a total of 16ml/hr (8ml/hr from continuous infusion and up to 8ml from PCEA). To match the total epidural volume in the programmed intermittent bolus group, they can receive additional 2ml

using a lock out period of 10 minutes. Because 4ml of epidural is bolused every 30 min and a PCEA bolus cannot coincide with the basal bolus doses, the shortend lock out period is necessary to make sure the patient can still receive the same four additional 2ml PCEA boluses as the continuous infusion group.

In addition, patients will be able to receive additional physician manual boluses, IV opioid medications from nursing staff, adjunct medications as per standard UCSF ERAS protocol. Hypotension and itching are some common adverse reactions to epidural analgesia; we will treat and document these episodes as per preexisting UCSF acute pain service epidural protocol.

Outcome measures will be total local anesthetic use (charted by nursing staff each shift as part of routine care), numeric rating scale (charted by nursing staff as part of routine care), total PCEA button presses (recorded on epidural pump), anxiety and functional measures (WHODAS2.0, brief pain inventory, HADS survey) to be measured on post operative day 1 and 2. Incidence of hypotension (charted by nursing staff as part of routine care).

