- Other (explain below)

Attach the telephone recruitment script in the Other Study Documents section of the Initial Review Submission Packet Form. If potential participants will initiate contact, attach the telephone screening script that will be used to provide more information about the study and determine if callers are eligible to participate.

10.6 RECRUITMENT PLAN: Based on the checkboxes you chose above, please provide a narrative describing your recruitment plan. We want to know:

- Who is conducting the search for potential participants, and how?
- How are potential subjects being approached for recruitment? By whom, and when?

If there will be more than one participant group (e.g. patients, healthy controls, caregivers, family members, providers, etc.), provide details about the recruitment plans for each group. (Recommended length - 100-250 words)

Patients eligible for this study will be informed of the study by an anesthesia provider participating in the study after their initial pre-operative anesthesia evaluation, but prior to day of surgery. Patient who meet the inclusion and non-inclusion criteria will receive a phone call from one of the study investigators explaining the study prior to the day of surgery. The consent form will be offered to them via mail or e-mail prior to the day of surgery to allow ample time to review and consider the patient's participation in the study. On the day of surgery, information about the study will be reiterated by an anesthesia provider and all questions will be answered prior to randomization.

10.7 * CONSENT METHODS: How will permission to participate (i.e., informed consent) be obtained from each potential participant. If there will be multiple groups and different plans for consenting each, check all that apply. See the orange Help bubble to the right for more detailed guidance. Participants will (check all that apply): (REQUIRED)

- Sign a consent form at the end of the consent discussion (signed consent)
- Provide online 'eConsent' using DocuSign or another E-Signature system
- Click through a link in a survey or email after reading about the study and then complete the study online (electronic consent)
- Be told about the study and be given a handout/information sheet and be asked if they agree to participate (verbal consent)
- Complete the study activities and turn in materials, as in the case of a completed survey that is placed in a drop box or mailed to the study team (implied consent)

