12.2 RISKS: Describe any anticipated risks and discomforts not listed above:

There are risks associated with the placement and use of epidural anesthesia. However, this study will only be performed in patients who have already consented to the current standard of care in the ERAS pathways. ERAS pathways routinely include the use of epidural anesthesia. Patients in this study will be seen daily by the study investigators as well as the acute pain service at Mission Bay. They will routinely be asked for side effects of regional anesthesia such as hypotension, itching and the catheter site will be inspected. In case of hypotension with a mean arterial blood pressure <60 mmHg, nursing orders to contact the primary service and the acute pain service for appropriate clinical response remain in place.

12.3

MINIMIZING RISKS: Describe the steps you have taken to minimize the risks/discomforts to subjects. Examples include:

- **designing the study to make use of procedures involving less risk when appropriate**
- **minimizing study procedures by taking advantage of clinical procedures conducted on the study participants**
- **mitigating risks by planning special monitoring or conducting supportive interventions for the study**
- **having a plan for evaluation and possible referral of subjects who report suicidal ideation**

There will be no interference with the care of the patient. The treatment of enrolled patients is not different from patients who do not participate in the study. We have already been using the programmed intermittent bolus function successfully in these patients, but it always happened at the discretion of the ordering anesthesia provider.

All procedures will be performed by or under direct supervision of an anesthesiologist attending as per current institutional protocol. Medication changes to the epidural solution will be handled by physicians only as per current institutional protocol.

Patient data remains confidential and de-identified. Only encrypted computers will be used for data collection and management.

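### Section 13.2 plans a between-arm look at outcomes after 44 completers, attaches no decision to it and does not limit who sees it, so investigators who see patients daily may learn which arm is ahead.

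*Combined protocol and SAP*

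**What the plan says.** Section 13.2 (Data and Safety Monitoring Plan) states, in the first person plural, that the authors are "planning on performing an interim analysis after 44 patients have completed the study to investigate whether there are any differences in outcomes". In full, the look is for "any differences in outcomes as well as adverse events reported between study groups". The plan text gives no stopping rule or other action tied to the outcome comparison, names no analyst outside the team, and does not say who receives the result. Individual adverse events are to "be brought immediately to the principal investigator for review". Section 13.3 asks "Will a Data and Safety Monitoring Board (DSMB) be established"; both Yes and No are printed in the available text, so the answer is unknown.

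The investigators' other roles are set out elsewhere:

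- **Recruitment (10.6):** eligible patients "will receive a phone call from one of the study investigators explaining the study".
- **Orders (7.9):** "The clinical investigator who enrolled the patient will write the epidural infusion orders".
- **Daily contact (12.2):** "Patients in this study will be seen daily by the study investigators as well as the acute pain service at Mission Bay".
- **Blinding (7.9):** the pump display is covered so that the patient does not learn the arm. No one else is described as blinded.

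Three statements limit these roles. Section 7.9 fixes the basal volume, demand dose and lockout by arm, and gives later pump management to the acute pain service rather than the investigators. Section 7.4 has nurses give the rescue opioid. Sections 10.6 and 10.8 place the study explanation and written consent before randomization.

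**The concern.** Knowing a patient's arm is one thing; knowing which arm is ahead part-way through is another. With 22 patients per arm, a sizeable difference can arise by chance. If people in contact with later patients learn of it, their expectations can push later data in the same direction, and those patients no longer give an independent test of the early difference.

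Some outcomes are open to this. Total opioid use, a primary outcome, includes rescue doses. Physician manual boluses are allowed under 7.9. Pain scores and satisfaction are reported by patients whom the investigators visit.

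This is separate from the type I error cost of an unadjusted interim test. It would remain even if no formal test were done at the look. Because the plan does nothing with the outcome comparison, the exposure buys no planned benefit.

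**Working it through.** **Inputs.** Interim after 44 completers (13.2). Enrolment 120, 60 per group; evaluable target 44 per group; effect size 0.6, power 80%, alpha 0.05 (9.3). Unpaired t-test for continuous outcomes (7.25). Equal split at the look, 22 per arm (assumption). The shift in later patients is also an assumption; the documents give no figure.

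**The plan's own figure.** n per group = 2 × (1.960 + 0.842)² / 0.6² = 43.6, so 44. The stated number reproduces as a two-sided calculation.

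**Patients exposed.** 120 − 44 = 76, and 76/120 = 63%. These have not yet completed. A few may already be enrolled or on treatment when the look is triggered, so 76 is an upper limit on those still to be enrolled. Against the evaluable target, 88 − 44 = 44, which is 50%.

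**What chance alone shows at the look.** Standard error of the standardized difference = √(2/22) = 0.302. With no true effect, by the normal approximation:

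- P(|d| ≥ 0.3) = 2 × [1 − Φ(0.3/0.302)] = 0.32
- P(|d| ≥ 0.5) = 2 × [1 − Φ(0.5/0.302)] = 0.097

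**Illustration of the effect on the final test.** Suppose there is no true effect, and that knowing the interim result moves an outcome by s SD between arms, in one fixed direction, in every later patient. Then:

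- bias b = s × (fraction of analysed patients after the look)
- noncentrality = b × √(n/2), with n per group
- false-positive rate = two-sided rejection probability of the noncentral t with 2n − 2 df

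| Assumed s (SD) | n = 60: bias (noncentrality) | n = 60: false positives (118 df) | n = 44: bias (noncentrality) | n = 44: false positives (86 df) |
|---|---|---|---|---|
| 0.1 | 0.063 (0.35) | 6.4% | 0.050 (0.23) | 5.6% |
| 0.2 | 0.127 (0.69) | 10.6% | 0.100 (0.47) | 7.5% |
| 0.3 | 0.190 (1.04) | 17.8% | 0.150 (0.70) | 10.7% |

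The n = 60 columns treat all 120 enrolled patients as analysed. The n = 44 columns use the evaluable target, since 9.3 adds the extra patients to cover incomplete data.

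**Sensitivity to the mechanism.** A fixed direction is not quite the mechanism described above, in which whichever arm leads is reinforced. Simulating that version with 60 per group gives roughly 10%, 18% and 30% for the same three shifts. If staff react only when |d| is at least 0.3, the rates are about 8%, 12% and 17%. The fixed-shift table is therefore not inflated by its simplification, but every row still depends on s.

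**The case against.** A reader might infer that the people who recruit, write orders and visit patients will certainly know the interim result, and that each role is a route to bias. The documents do not support that reading.

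- **Who knows.** That the investigators learn the result is an inference from the first-person wording and the lack of a stated restriction. The answer in 13.3 is unreadable, so it cannot be said that no board exists.
- **Orders.** The initial settings are fixed by arm, so the order writer has little room for discretion.
- **Pump and rescue.** The acute pain service runs the pumps after set-up, nurses give rescue opioid, and nurses chart pain scores and local anesthetic use. Nothing says that either group is told the result.
- **Patient reports.** Satisfaction and button presses come from a patient kept blinded.
- **Recruitment.** It precedes randomization. A change in how the study is presented, or in who joins, alters case mix in both arms and does not by itself bias the difference between them.
- **Added harm.** The team already aims to prove the bolus method superior (7.3) and reports using it successfully (12.3). The documents give no basis for the size of any further shift caused by interim knowledge.

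All of this stands, and it narrows the point. It does not close it: investigators still see patients daily, physicians may give manual boluses, and nothing prevents informal spread of the result to the pain service and ward nurses. It is also fair to say that follow-up is short and both delivery modes are already in use locally, which argues for a modest remedy.

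**Conclusion.** The point holds in a limited form. Section 13.2 plans a between-arm outcome comparison that no decision uses and whose circulation is not restricted. As written, investigators in daily contact with patients of known arm may learn which arm is ahead while up to 76 of 120 planned patients have not completed.

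The bias cannot be sized from the documents. The ranges of about 6–18% (60 per group) and 6–11% (44 per group) follow wholly from assumed fixed shifts of 0.1 to 0.3 SD and should be read as illustration, not as a forecast. The change is worth making because it removes an avoidable route to bias and gives up nothing the plan relies on.

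**What to change.** In 13.2:

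1. Delete the between-arm comparison of efficacy outcomes at 44 patients.
2. Limit the look to adverse events and arm-blind checks, namely data completeness and the pooled spread of the outcomes.
3. State that hypotension is reviewed pooled across arms at this look. It is both an adverse reaction (7.9) and a secondary outcome (7.4), so a by-arm table would disclose an outcome. Individual adverse events continue to go to the principal investigator as now planned.

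The cost is one paragraph, with no extra staff. The downside is that investigators see no early efficacy result. Keeping the comparison but giving it to someone who does not enrol or visit patients is possible, but it would need that person and a stopping rule, and the plan text provides neither.

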14.0 Confidentiality, Privacy, and Data Security

14.1 PROTECTING PRIVACY: Indicate how subject privacy will be protected:

- Conduct conversations about the research in a private room
- Ask the subject how they wish to be communicated with – what phone numbers can be called, can messages be left, can they receive mail about the study at home, etc.
- Take special measures to ensure that data collected about sensitive issues do not get added to their medical records or shared with others without the subject's permission
- Other methods (describe below)

14.2 SENSITIVE DATA: Do any of the instruments ask about illegal or stigmatized behavior:

Yes No

14.3 CONSEQUENCES OF A LOSS OF PRIVACY OR CONFIDENTIALITY: Could a breach of privacy or confidentiality result in any significant consequences to participants, such as criminal or civil liability, loss of state or federal benefits, or be damaging to the participant's financial standing, employability, or reputation:

Yes No

14.4 EXTRA CONFIDENTIALITY MEASURES: Explain any extra steps that will be taken to assure confidentiality and protect identifiable information from improper use and disclosure, if any:

All patient identifiers will be decoupled from the remainder of the data as soon as possible to minimize loss of confidentiality through the study.

14.5 * REPORTABILITY: Do you anticipate that this study may collect information that State or Federal law requires to be reported to other officials, such as elder abuse, child abuse, or threat to self or others: (REQUIRED)

Yes No

14.6 CERTIFICATE OF CONFIDENTIALITY: Will this study obtain a Certificate of Confidentiality:

Yes No

14.7 SHARING OF RESEARCH RESULTS: Will there be any sharing of **EXPERIMENTAL** research test results with subjects or their care providers:

Yes No

14.8 * IDENTIFIERS: Will personal identifiers be included in research records: (REQUIRED)

Yes No

Check all the identifiers that may be included:

- Names
- Dates
- Postal addresses
- Phone numbers
- Fax numbers
- Email addresses
- Social Security Numbers*
- Medical record numbers
- Health plan numbers
- Account numbers
- License or certificate numbers
- Vehicle ID numbers
- Device identifiers or serial numbers
- Web URLs
- IP address numbers
- Biometric identifiers
- Facial photos or other identifiable images
- Any other unique identifier

* Could study records include ANY photos or images (even 'unidentifiable' ones):
(REQUIRED)

Yes No

14.9 DATA DISCLOSURE: Will identifiable information be shared with outside groups:

Yes No

14.11 * DATA COLLECTION AND STORAGE: (check all that apply): **(REQUIRED)**

Collection methods:

- Paper-based (surveys, logs, diaries, etc.)
- Electronic case report forms (CRFs), such as OnCore or another clinical trial management portal
- Web-based online surveys or computer-assisted interview tool
- Mobile applications (mobile or tablet-based)
- Wearable devices
- Audio/video recordings
- Other:

* Data will be collected/stored in systems owned by (check all that apply):
(REQUIRED)

- UCSF
- SF VAMC
- Amazon (Amazon Cloud)
- Other academic institution
- 3rd party vendor (business entity)
- Other (explain below)

14.12 DATA SECURITY: Indicate how data are kept secure and protected from improper use and

disclosure (check all that apply): NOTE: Whenever possible, do not store subject identifiers on laptops, PDAs, or other portable devices. If you collect subject identifiers on portable devices, you MUST encrypt the devices.

- Data are stored securely in My Research
- Data are coded; data key is destroyed at end of study
- Data are coded; data key is kept separately and securely
- Data are kept in a locked file cabinet
- Data are kept in a locked office or suite
- Electronic data are protected with a password
- Data are stored on a secure network
- Data are collected/stored using REDCap or REDCap Survey
- Data are securely stored in OnCore

14.13 * DATA SECURITY: Confirm below that you will keep data confidential: (REQUIRED) I will keep any data sets that include identifiers secure and protected from improper use and disclosure by using methods such as:

- **Physical Security – Keeping data in locked file cabinets, locked offices, locked suites, and physically securing computers and servers.**
- **Electronic Security – Following UCSF minimum security standards for electronic information resources, which includes (but is not limited to): not storing identifiers on portable devices like laptops or flash drives if they are unencrypted, encrypting portable devices, and storing data in password-protected files and on secure networks.**

Yes

14.15 * HIPAA APPLICABILITY: Study data will be: (REQUIRED)

- Derived from the Integrated Data Repository (IDR) or The Health Record Data Service (THREDS) at SFGH
- Derived from a medical record (e.g. APeX, OnCore, etc. Identify source below)
- Added to the hospital or clinical medical record
- Created or collected as part of health care
- Obtained from the subject, including interviews, questionnaires
- Obtained ONLY from a foreign country or countries
- Obtained ONLY from records open to the public
- Obtained from existing research records
- None of the above

In addition to signing a consent form, each subject will have to sign the UCSF Research Subject Authorization Form (HIPAA Form). NEW REQUIREMENT - This form should be uploaded in the Other Study Documents section of the Initial Review Submission Packet Form. Failure to have the signed HIPAA Authorization is one of the most common findings from QIU Routine Site Visits and can result in a Serious Noncompliance determination. Please call the IRB office at [contact] if you have questions about HIPAA research requirements.

14.16 * HIPAA - PERMISSION TO ACCESS SENSITIVE DATA: Does the research require access to any of the following types of health information from the medical record: (check all that apply) (REQUIRED)

- Drug or alcohol abuse, diagnosis or treatment
- HIV/AIDS testing information
- Genetic testing information
- Mental health diagnosis or treatment
- None of the above

Important note: Ensure that participants DO NOT initial any of the lines in Section C of the HIPAA authorization form during the consent process.

